**Table 8-1 Assessment Windows for Scheduled Visits**

Visit	Target Study Day	Study Day Interval
ECGs and hemodynamics:		
Baseline	1	Study Day $\leq 1$ (prior to the first dose)
Week 24	169	$148 \leq$ Study Day $\leq 190$
Clinical laboratory assessments and NT-proBNP:		
Baseline	1	Study Day $\leq 1$ (prior to the first dose)
Week 12	85	$2 <$ Study Day $\leq 127$
Week 24	169	$127 <$ Study Day $\leq 211$
Week 36	253	$211 <$ Study Day $\leq 337$
Week 60	421	$337 <$ Study Day $\leq 505$
Weeks 84, 108, etc	589, 757, etc	(Target Study Day $\pm 84$ days)
6MWT, WHO FC, and vital signs:		
Baseline	1	Study Day $\leq 1$ (prior to the first dose)
Week 4	29	$15 \leq$ Study Day $\leq 43$
Week 8	57	$43 <$ Study Day $\leq 71$
Week 12	85	$71 <$ Study Day $\leq 127$
Week 24	169	$127 <$ Study Day $\leq 211$
Week 36	253	$211 <$ Study Day $\leq 295$
Weeks 48, 60, etc	337, 421, etc	(Target Study Day $\pm 42$ days)

Note: Study Day = (Assessment Date) - (First Dosing Date) + 1

### **8.6.2 Multiple Evaluations within the Same Analysis Window**

After all the observations have been slotted based on the table above, if there are multiple valid observations for an assessment within an assigned analysis visit window, only 1 of these observations will be used for summary statistics and analyses. The observation to be used is determined using the following hierarchy (in decreasing order):

- The observation closest to the target study day
- The later observation, if 2 observations are equally close to the target study day

For missing values prior to Week 48 where the LOCF algorithm is applied, it is always the last valid observation on treatment carried forward, even though this might not be the observation obtained by the above hierarchy and used in the summaries by visit window.

## 9 STUDY POPULATION

Detailed definitions for analysis populations (ITT, Per-Protocol, and Safety Populations) are provided in Section 6. Unless otherwise specified, all efficacy analyses will be performed on the ITT Population and all safety analyses will be based on the Safety Population. In the ITT Population, the treatment assignment is based on the assignment upon randomization. In the Safety Population, the treatment assignment is based on the actual treatment the subject received. Study population will be summarized by the treatment group in the ITT population and overall.

The comparability between the 2 treatment groups will be checked for demographic and Baseline characteristics. The p-values from Fisher's exact test (for discrete variables), group t-test, or Wilcoxon rank sum test (for continuous variables) will be included in summaries but are not intended to be used to test formal hypotheses. For these comparisons, missing or unknown values will be excluded from the calculations.

### 9.1 SUBJECT ACCOUNTABILITY

All subjects' disposition information will be listed, including the study population the subjects belong to, whether or not subjects completed the study drug treatment, reason study drug was stopped, whether or not subjects completed at least 24 weeks of study assessments, primary reason for not completing 24 weeks of assessments, whether or not subjects completed the study, reason for not completing the study, and whether or not subjects rolled over to the open-label extension study (TDE-PH-311).

The listing of subject accountability will include dates of informed consent, randomization, first study drug dose, last study drug dose, last dose week, and last assessment week.

Whether subjects received study drug; whether subjects completed the Weeks 4, 8, 12, and 24 assessments, and every 12-week follow-up assessment thereafter; study drug termination status; and study discontinuation status will be summarized by treatment group and overall.

Information regarding whether each subject is included in each analysis population (see Section 6) will be listed. If a subject is not included in a particular analysis population, the reason for exclusion will be noted on the listing. Also noted on the listing will be the

randomized treatment assignment and the actual treatment subjects have received. The summary will include the frequency and percentage of all subjects in each analysis population by treatment group and overall.

All stratification information used in the random assignment of subjects to treatment group (from the central randomization database) will be listed, including date and time of randomization, background PAH therapy, Baseline walk distance category, whether or not the treatment is unblinded, and if so, date/time of blind break. For observations where any stratification information has been corrected, both the original and corrected information will be listed. Background PAH therapy and Baseline walk distance used for randomization stratification will be summarized by treatment group and compared using Fisher's exact test or Wilcoxon rank sum test, as appropriate.

## 9.2 PROTOCOL DEVIATIONS

The status of the entry criteria will be listed for all subjects. The listing will include the date of the initial screening assessment and a list of any specific entry criteria not met. Entry criteria violations will be summarized by treatment group and overall.

Additional protocol deviations will be documented throughout the study, and protocol deviations and their severity categories will be summarized by treatment group and included in the data listing.

## 9.3 OTHER DESCRIPTIONS OF STUDY POPULATIONS

### 9.3.1 *Demographics*

All demographic data will be listed for all subjects, including country, age at randomization, sex, ethnicity, race, weight, height, and Body Mass Index (BMI). Age, age category (<65 years versus  $\geq$ 65 years), sex, ethnicity, race, weight, height, and BMI will be summarized by treatment group. The summary will include p-values (2-sided) from Fisher's exact test (for age category, sex, ethnicity, and each race), group t-test, or Wilcoxon rank sum test (for age, weight, height, and BMI) comparing treatment groups.

**9.3.2 Medical History and PAH History**

All significant past or ongoing medical conditions will be listed for all subjects. The listing will include the Medical Dictionary for Regulatory Activities (MedDRA) system organ class (SOC) and preferred term (PT) for each condition listed. These medical conditions will be summarized by PT within each SOC by treatment group.

Information related to subjects' PAH history will be listed. The listing will include the date of initial PAH diagnosis, time since diagnosis at randomization, and etiology of PAH. A separate listing will include details of the subjects' background PAH therapy (eg, PDE5-I/sGC stimulator or ERA use).

Time since diagnosis and etiology of PAH will be summarized by treatment group. The summary will include p-values (2-sided) from Fisher's exact test (for etiology of PAH) or Wilcoxon rank sum test (for time since diagnosis) comparing treatment groups.

Background PAH therapy at Baseline will be summarized by treatment group. The summary will include the number and percentage of each PAH therapy use, time on background PAH therapy, and the total daily dose of the background PAH therapy.

**9.3.3 Concomitant Medications**

All concomitant medications specified on the eCRF will be mapped to a standard term using the WHO Drug Dictionary (WHO-DD).

The standard name and verbatim term of all concomitant medications will be listed for all subjects. This listing will include the date started (or indication that drug was ongoing at randomization), date discontinued (or indication that drug was ongoing at end of study), and the condition treated/indications. If a subject received no medications, this will be indicated in the listing. The summary of concomitant medications will include the frequency and percentage of subjects in each treatment group receiving each drug (by coded standard name). Concomitant medications ongoing at Baseline and those added during the study will be summarized separately.

Changes to ERA, PDE5-I, and sGC stimulator dosing that are collected separately from the concomitant medication page will be listed.

## 10 EFFICACY ANALYSES

Except where otherwise noted, all efficacy analyses will only be performed on the ITT Population (see Section 6).

### 10.1 PRIMARY EFFICACY MEASURES

#### 10.1.1 *Time to Clinical Worsening*

Clinical worsening is defined as the occurrence of any of the following:

- Death (all causes)
- Hospitalization due to worsening PAH defined as:
  - Non-elective hospitalization lasting at least 24 hours in duration caused by clinical conditions directly related to PAH and/or right heart failure; or
  - Lung or heart transplantation; or
  - Atrial septostomy
- Initiation of an inhaled or infused prostacyclin for the treatment of worsening PAH
- Disease progression (all criteria required):
  - A decrease in 6MWD of at least 15% from Baseline (or too ill to walk) directly related to PAH progression with other co-morbidities ruled out, confirmed by 2 6MWTs performed on different days.
  - Worsening of PAH symptoms, which must include either:
    - An increase in FC since Baseline or
    - Appearance or worsening of symptoms of right heart failure since Baseline
- Unsatisfactory long-term clinical response (all criteria required)
  - Randomized to receive study drug for at least 24 weeks
  - A decrease from Baseline in 6MWD at Week 24 and beyond at 2 consecutive visits on different days
  - Sustained WHO FC III or IV symptoms for at least 24 weeks, consecutively

##### 10.1.1.1 *Hypothesis*

The study is designed to determine the efficacy of UT-15C compared with placebo in subjects with PAH. The null hypothesis tested for the primary endpoint of time to adjudicated clinical worsening is that there is no difference in hazard ratio in the time to clinical worsening of PAH when treated with UT-15C compared with placebo:

$$H_0: \text{hazard ratio} = 1$$

The 2-sided alternative hypothesis is that there is a difference:

$$H_a: \text{hazard ratio} \neq 1$$

Due to the alpha spending on interim analysis, for the final analysis, the significance level for the primary efficacy analysis of time to adjudicated clinical worsening is 0.044.

#### ***10.1.1.2 Primary Efficacy Analyses***

Data on the Clinical Worsening Assessment page of the eCRF will be used in determining clinical worsening status. Investigator-reported clinical worsening events will be reported directly from the eCRF data, regardless of the outcome of the adjudication committee review. An independent adjudication committee will be utilized to adjudicate all investigator-reported clinical worsening events. Adjudicated clinical worsening events will be reported using data received from the adjudication committee.

Subjects who discontinue study drug for reasons other than clinical worsening will be censored at the time of discontinuation of the study drug. Non-fatal clinical worsening events that occur more than 7 days after permanent study drug discontinuation will not be included in the summary and analysis of clinical worsening events. However, all deaths within the study follow-up period (30 days after the last study drug dose) will be included as clinical worsening events. Time to clinical worsening will be summarized by treatment group using product-limit estimates calculated by the Kaplan-Meier method, and displayed graphically as Kaplan-Meier curves. A tabular summary of this analysis will include the number of subjects at risk (sample size), estimated median duration, and a 95% confidence interval for the median duration for each treatment group.

For the primary efficacy analysis of time to adjudicated clinical worsening, the log-rank test adjusted for the type of background therapy (PDE5-I or sGC stimulator versus ERA) and the Baseline 6MWD ( $\leq 350$  meters versus  $> 350$  meters) will be used to calculate the p-value for treatment differences in the ITT Population.

The SAS Procedure LIFETEST will be used. The pseudo SAS statements are listed below:

```
proc lifetest;
  time TimeToWorsening*Censor_Status(1);
  strata BGTX B_6MWD / group=Treatment test=all;
run;
```

where BGTX variable denotes the background therapy and B\_6MWD denotes the Baseline 6MWD category ( $\leq 350$  meters versus  $> 350$  meters).

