3.5 ESTIMATED STUDY DURATION

Subjects will remain in the study until they either experience a clinical worsening event, discontinue the study for any other reason, or approximately 205 adjudicated clinical worsening events have occurred. It is estimated that the overall study duration will last for 4 years; however, this is dependent on the rate of clinical worsening events.

Subjects that discontinue and do not roll into the open-label extension study (TDE-PH-311) will be contacted approximately 30 days (± 5 days) after study drug discontinuation to confirm their survival status. Subjects that complete TDE-PH-310 and roll in to the open-label extension study will also be contacted approximately 30 days (± 5 days) after study drug discontinuation in study TDE-PH-310 to confirm their survival status.

Subjects may also continue to be contacted after the final study visit to assess ongoing AEs/SAEs (see Section 9.2 for additional details).

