5 DATA COLLECTION AND FOLLOW-UP OF SUBJECTS

Survival status for discontinued subjects will be collected every 6 months from the date of discontinuation via telephone calls or other methods as described below. The collection of vital status should include whether or not the subject is alive.

- If dead, the date of death must be obtained.
- If alive, the last known date the subject was confirmed to be alive must be provided.
- For those subjects who are lost to follow-up, the last known date that the subject was confirmed to be alive will be their date of the last contact with the site.

Methods to confirm subjects' survival status other than the recommended telephone calls every 6 months, may include and are not limited to, in-person study visits, searching of hospital records, and searching local and/or national public registries following applicable laws and regulations.

Any AEs that are spontaneously reported by the subject that occur on the commercially-available United Therapeutics drug should not be submitted as part of the study, rather, they will be subject to AE/SAE reporting under local government post-marketing AE/SAE reporting requirements.

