### 5 SAMPLE SIZE CONSIDERATIONS

Approximately 205 adjudicated clinical worsening events will provide at least 90% power with a type I error rate of 0.05 (2-sided hypothesis) to detect a difference in the time to clinical worsening between treatment groups, assuming exponential distributions and an underlying hazard ratio of 0.62. Assuming a placebo median event time of 32 months (which corresponds to an event rate of 23% at Month 12), this hazard ratio corresponds to a median time to event of 51 months for the UT-15C group (which corresponds to an event rate of 15% at Month 12). Further assuming subject accrual is completed during the first 3 years with a 10% dropout rate at the end of the study, a total sample size of at least 610 subjects with a maximum of 850 subjects is expected to generate approximately 205 adjudicated clinical worsening events over the course of the study.

The primary efficacy endpoint of time to adjudicated clinical worsening events will be tested at an interim analysis when 75% of total adjudicated clinical worsening events have occurred with an alpha level of 0.020, and at the final analysis at an alpha of 0.044 with the overall Type I error rate at 0.05. Efficacy boundaries for early stopping of the study for efficacy are calculated based on O'Brien-Fleming alpha-spending function.

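### SAP 10.1.1.2 counts events for 7 or 30 days after study drug stops but censors event-free subjects at the stop, so remaining at risk depends on the outcome; the effect is small

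*SAP*

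**What the plan says.** **When events stop counting (SAP 10.1.1.2).** Non-fatal worsening is dropped only if it occurs more than 7 days after permanent discontinuation. For deaths the window is longer: "However, all deaths within the study follow-up period (30 days after the last study drug dose) will be included as clinical worsening events".

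**When event-free subjects leave the risk set.** Three sections give different dates.
- SAP 10.1.1.2: "Subjects who discontinue study drug for reasons other than clinical worsening will be censored at the time of discontinuation of the study drug".
- SAP 8.3.1: the last known dose for subjects without an adjudicated event, and for early dropouts the last assessment before down-titration or stopping.
- SAP 8.5: the last assessment date, with no on-drug limit.

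None of them extends event-free follow-up to day 7 or day 30.

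**What is collected after the stop.** Protocol 3.5 requires a survival contact at about 30 days (± 5) for subjects who discontinue. It covers rollovers too: "Subjects that complete TDE-PH-310 and roll in to the open-label extension study will also be contacted approximately 30 days" after study drug stops. SAP section 3 has all remaining subjects move to the open-label extension once about 205 adjudicated events have occurred. Under Protocol 7.5, former placebo subjects start UT-15C there.

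**The concern.** Take two subjects who stop drug on the same day. One dies on day 20 and is an event on day 20. The other is alive at the day-30 contact and is censored on day 0. Under SAP 10.1.1.2 and 8.3.1, the only stoppers still in the risk set after the stop are those who will have an event. Independent censoring fails by construction in that interval.

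This reaches the primary log-rank test and the Cox model. It also reaches time to death during the study, because SAP 10.1.1.3 analyses that component in the same way as the composite. If more UT-15C than placebo subjects stop, the extra events fall more heavily on UT-15C.

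A second question concerns the switch to TDE-PH-311. A death within 30 days of the last TDE-PH-310 dose may occur after a placebo subject has started active drug. It matters for subjects without an adjudicated event: those who switch at closure, and those who rolled over on an event that the Medical Monitor accepted and the adjudication committee later rejected.

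The sensitivity analyses in SAP 10.1.1.3 do not test any of this. They recode dropouts as events or use the Per-protocol Population.

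**Working it through.** **1. The plan's own figure.** SAP section 5 uses 205 events, an "underlying hazard ratio of 0.62", two-sided 0.05 overall, and tests "at the final analysis at an alpha of 0.044".
- Schoenfeld: power = Φ(√205/2 × |ln 0.62| − z) = Φ(7.159 × 0.478 − 1.960) = Φ(1.462) = 92.8%. At 0.044 (z = 2.014) it is 92.0%.
- Freedman: √205 × 0.38/1.62 = 3.359, giving 91.9% and 91.1%.

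The stated power of at least 90% reproduces.

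**2. Expected extra events, 610 subjects.**
- Dropouts: 10% (SAP section 5), so 61.
- Event-free at closure: 610 − 205 − 61 = 344.
- Death rate (assumption): 93.6% one-year survival in the earlier open-label study (Protocol 1.2.4). Thirty-day risk = 1 − exp(30 × ln 0.936/365) = 0.54%.
- Non-fatal hazard: "Assuming a placebo median event time of 32 months" gives ln 2/32 = 0.02166 per month. Less the death hazard, 0.06614/12 = 0.00551, this leaves 0.01615 per month, or 0.37% over 7 days.

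| Source | Same hazard after stop | Five-fold in dropouts (assumption) |
|---|---|---|
| Deaths, 344 switchers, 30 days | 1.9 | 1.9 |
| Deaths, 61 dropouts, 30 days | 0.3 | 1.6 |
| Non-fatal, 61 dropouts, 7 days | 0.2 | 1.1 |
| Total | 2.4 (1.2% of 205) | 4.6 (2.3% of 205) |

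At the maximum of 850 there are 85 dropouts and 850 − 205 − 85 = 560 switchers, with 3.0 switcher deaths. Scaling the dropout rows by 85/61 gives totals of about 3.8 and 6.9.

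**3. Effect on the hazard ratio.** Simulation: 610 subjects, exponential times, true HR 0.62, 36-month accrual, closure at 48 months, 3,000 runs per scenario, unstratified log-rank with its one-step HR. Dropout percentages are reached at 30 months on study. Dropouts revert to the placebo hazard times the multiplier. Three rules were compared:
- plan: late events count, event-free subjects are censored at the stop;
- matched: the same events count, event-free subjects stay at risk 30 days;
- strict: events and censoring both end at the stop.

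| Dropout UT-15C/placebo | Multiplier | Plan | Matched | Strict |
|---|---|---|---|---|
| 10%/10% | 1 | 0.620 | 0.620 | 0.619 |
| 10%/10% | 5 | 0.623 | 0.623 | 0.620 |
| 22%/14% | 1 | 0.623 | 0.621 | 0.621 |
| 22%/14% | 5 | 0.631 | 0.629 | 0.621 |
| 30%/15% | 1 | 0.628 | 0.624 | 0.624 |
| 30%/15% | 5 | 0.641 | 0.637 | 0.624 |

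The 22%/14% split is the discontinuation seen in TDE-PH-301 (Protocol 1.2.4); 30%/15% is a stress case without a source. The largest gap between plan and strict is 0.641 − 0.624 = 0.017. Of that, 0.641 − 0.637 = 0.004 is removed by matching the time at risk; the rest comes from counting late events at all. The largest power loss, plan against strict, is 93.5% − 91.5% = 2 points.

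**4. Type I error.** Under HR 1.00 and the same six settings, the plan rule rejects in 0.039 to 0.048 of runs at nominal 0.044. The simulation standard error is √(0.044 × 0.956/3000) = 0.0037, so no inflation is visible.

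**The case against.** The strongest reply is that most of the shift is not censoring bias. Late deaths and hospitalisations are real events, and counting them is a defensible choice; lengthening the time at risk to match moves the HR by about 0.004. That stands. The rule is worth correcting because it is avoidable in a confirmatory analysis, not because it distorts the result much.

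Several stronger readings are tempting, and the documents do not support them.
- A reader might infer a material bias from a ten-fold hazard after stopping, which can give about 14 extra events and an HR near 0.65. Nothing in the documents supports ten-fold. The 22%/14% split comes from a 16-week twice-daily trial that began with 1 mg steps; Protocol 1.2.4 reports no adverse-event discontinuations among the 23 subjects there who had 0.25 mg tablets at randomization. This plan assumes 10% dropout.
- A reader might infer that event-free stoppers never contribute post-drug time. SAP 8.5 has no on-drug limit, and subjects who stop before Week 24 are encouraged to attend visits to Week 24, so under that section some would contribute it.
- A reader might take it as settled that deaths after rollover count. That follows from the unrestricted death rule and the day-30 contact, but SAP 10.1.1.2 does not mention rollovers. SAP 10.1.1.3 names them only for the separate death analysis to the end of the study.
- A reader might extend the point to the vital-status sub-study, where for lost subjects "the last known date that the subject was confirmed to be alive will be their date of the last contact with the site". That analysis is separate and supportive, and censoring at a registry search date would assume that no death record means alive.

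**Conclusion.** The mismatch is real. SAP 10.1.1.2 counts events to day 7 or day 30, while SAP 10.1.1.2 and 8.3.1 end event-free follow-up at or before the stop, and no section closes the gap. SAP 8.5 adds a conflicting date rather than a cure.

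The size is minor: about 2 to 5 extra events of 205 with 610 subjects, and an HR shift of at most about 0.02. The direction is against UT-15C when more UT-15C subjects stop. No false-positive risk was found. These figures rest on the earlier open-label death rate, the plan's 10% dropout for the counts, and a post-stop hazard of up to five-fold; the last is an assumption. Handling of deaths after the open-label switch is a gap in the SAP's wording, worth about 1.9 deaths across both arms if 344 subjects switch.

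**What to change.** Before unblinding, define one cut-off date per subject in SAP 8.3.1, 8.5 and 10.1.1.2 and use it for both events and censoring in the primary analysis. Two workable choices are drug stop, or last dose + 7 days for every component, with event-free subjects kept at risk to the same date. Cut it at the first TDE-PH-311 dose. This date replaces the three now given.

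Do not simply extend censoring to last dose + 30 days. With the 7-day limit on non-fatal events, days 8 to 30 would be time in which only death can count, and the day-30 contact establishes survival, not freedom from the composite.

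Report deaths to day 30 in the death analysis, with survivors followed to the contact already required by Protocol 3.5, and state there how deaths after open-label start are handled.

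The cost is SAP wording and one derived date, with no new data collection. The downside is that a few late deaths move from the primary composite to the death analyses.
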